### 9.2.1.3 End of Treatment and Follow-up Tumor Imaging

**Note: As per Amendment 04, there is no protocol specified imaging after the Week 9 assessment. This section has been updated accordingly.**

For participants who discontinue study treatment before the Week 9 imaging assessment for efficacy analysis, tumor imaging should be performed at the time of treatment discontinuation ( $\pm$ 4 week window). If previous imaging was obtained within 4 weeks prior to the date of discontinuation, then imaging at treatment discontinuation is not mandatory. For participants who discontinue study treatment due to radiographic disease progression, this is the final required tumor imaging.

### 9.2.1.4 Second Course Phase Tumor Imaging

**Note: As of Amendment 04, Second Course imaging will be assessed by the investigator and iRECIST is no longer applicable; transmission of images to the central review of imaging is no longer required. Disease assessment will be performed by the investigator per SoC for the disease and local guidelines. This section has been updated accordingly.**

Tumor imaging must be performed within 28 days prior to restarting treatment with pembrolizumab plus epacadostat, or pembrolizumab monotherapy. Before a participant may enter Second Course Phase, radiographic PD must have occurred. The PD imaging may also be used as the Second Course baseline imaging if it is within 28 days prior to restarting treatment.

Local reading (investigator assessment with site radiology reading) will be used to determine eligibility. Imaging for disease assessments will be performed by site investigator/radiology assessment as per SoC for the disease and local guidelines; only the date of scans performed as per SoC needs to be documented in the eCRF.

### 9.2.1.5 RECIST 1.1 Assessment of Disease

RECIST 1.1 will be used as the primary measure for assessment of tumor response, date of disease progression, and as a basis for all protocol guidelines related to disease status (eg, discontinuation of study treatment). Although RECIST 1.1 references a maximum of 5 target lesions in total and 2 per organ, this protocol allows a maximum of 10 target lesions in total and 5 per organ, if clinically relevant to enable a broader sampling of tumor burden.

### 9.2.1.6 iRECIST Assessment of Disease (Group 1 and 2)

**NOTE: As of Amendment 04, this section is no longer applicable; iRECIST data will no longer be collected. Participants with radiographic disease progression as determined by RECIST 1.1 will discontinue from the study and be followed for safety monitoring, as detailed in Section 9.3; no confirmatory scans are required.**

iRECIST is based on RECIST 1.1, but adapted to account for the unique tumor response seen with immunotherapeutic agents and therefore is only required for participants in Group 1 and Group 2. iRECIST will be used by the investigator to assess tumor response and progression, and make treatment decisions. When clinically stable, Group 1 and 2 participants should not be discontinued until progression is confirmed by the investigator, working with local radiology, according to the rules outlined in Appendix 8. This allowance to continue treatment despite initial radiologic PD takes into account the observation that some participants can have a transient tumor flare in the first few months after the start of immunotherapy, and then experience subsequent disease response. These data will be captured in the clinical database.

Clinical stability is defined as the following:

- Absence of symptoms and signs indicating clinically significant progression of disease
- No decline in ECOG PS
- No requirements for intensified management, including increased analgesia, radiation, or other palliative care.

Any participant deemed **clinically unstable** should be discontinued from study treatment at central verification of site-assessed first radiologic evidence of PD and is not required to have repeat tumor imaging for confirmation of PD by iRECIST.

If the investigator decides to continue treatment, the participant may continue to receive study treatment and the tumor assessment should be repeated 4 to 8 weeks later to confirm PD by iRECIST, per investigator assessment. Images should continue to be sent in to the central imaging vendor for potential retrospective BICR.

If repeat imaging does not confirm PD per iRECIST, as assessed by the investigator, and the participant continues to be clinically stable, study treatment may continue and follow the regular imaging schedule. If PD is confirmed, participants will be discontinued from study treatment.

[figure not shown]

If a participant has confirmed radiographic progression (iCPD) as defined in Appendix 8, study treatment should be discontinued; however, if the participant is achieving a clinically meaningful benefit, an exception to continue study treatment may be considered following consultation with MSD. In this case, if study treatment is continued, tumor imaging should continue to be performed following the intervals as outlined in Section 2 and be submitted to the central imaging vendor.

A description of the adaptations and iRECIST process is provided in Appendix 8, with additional details in the iRECIST publication [Seymour, L., et al 2017]. A summary of imaging and treatment requirements after first radiologic evidence of progression is provided in Table 14 and illustrated as a flowchart in Figure 2.

Table 14 Imaging and Treatment after First Radiologic Evidence of Progressive Disease

	Clinically Stable		Clinically Unstable	
	Imaging	Treatment	Imaging	Treatment
First radiologic evidence of PD by RECIST 1.1 that has been verified by BICR	Repeat imaging at 4 to 8 weeks to confirm PD	May continue study treatment at the investigator's discretion while awaiting confirmatory tumor imaging by site by iRECIST.	Repeat imaging at 4 to 8 weeks to confirm PD per investigator's discretion only	Discontinue treatment
Repeat tumor imaging confirms PD (iCPD) by iRECIST per investigator assessment	No additional imaging required	Discontinue treatment (exception is possible upon consultation with MSD)	No additional imaging required	Not applicable
Repeat tumor imaging shows iUPD by iRECIST per investigator assessment	Repeat imaging at 4 to 8 weeks to confirm PD. May occur at next regularly scheduled imaging visit.	Continue study treatment at the investigator's discretion.	Repeat imaging at 4 to 8 weeks to confirm PD per investigator's discretion only.	Discontinue treatment
Repeat tumor imaging shows iSD, iPR or iCR by iRECIST per investigator assessment	Continue regularly scheduled imaging assessments	Continue study treatment at the investigator's discretion	Continue regularly scheduled imaging assessments	May restart study treatment if condition has improved and/or clinically stable per investigator's discretion. Next tumor image should occur according to the regular imaging schedule
Abbreviations: BICR = blinded independent central review; iCPD = iRECIST confirmed progressive disease; iCR = iRECIST complete response; iRECIST = modified Response Evaluation Criteria in Solid Tumors 1.1 for immune-based therapeutics; iPR = immune partial response; iSD = iRECIST stable disease; iUPD = iRECIST unconfirmed progressive disease; PD = progressive disease; RECIST 1.1 = Response Evaluation Criteria in Solid Tumors 1.1; VOP = verification of progression. Note: If progression has been centrally verified, further management is by the site, based on iRECIST. Any further imaging should still be submitted to the central imaging vendor, but no rapid review will occur. If RECIST 1.1 disease progression has not been centrally verified, ideally the site should continue treatment. Whether or not treatment continues, imaging should be collected and submitted to the central imaging vendor with VOP request until RECIST 1.1 progression is verified by BICR.				

Abbreviations: iRECIST = modified Response Evaluation Criteria in Solid Tumors 1.1 for immune-based therapeutics; PD = progressive disease; RECIST 1.1 = Response Evaluation Criteria in Solid Tumors 1.1.

Figure 2 Imaging and Treatment for Clinically Stable Group 1 and 2 Participants after First Radiologic Evidence of Disease Progression Assessed by the Investigator

### 9.2.2 Patient Reported Outcomes

**Note: As of Amendment 04, PROs will no longer be collected after the first on-study imaging assessment at Week 9.**

The EQ-5D, EORTC QLQ-C30 and EORTC QLQ-H&N35 questionnaires will be administered by trained site personnel and completed electronically by participants in the following order: EQ-5D first, then EORTC QLQ-C30, followed by EORTC QLQ-H&N35. The questionnaires should be administered prior to dosing at Cycle 1, Cycle 2, Cycle 3, and Cycle 4.

It is best practice and strongly recommended that electronic patient-reported outcomes (ePROs) are administered to randomized participants prior to drug administration, AE evaluation, and disease status notification. If the participant does not complete the ePROs at a scheduled time point, the MISS\_MODE form must be completed to capture the reason the assessment was not performed.

### 9.2.3 Health Care Resource Utilization

All-cause hospitalizations and emergency room visits must be reported in the eCRF, from the time of treatment allocation/randomization through 90 days following cessation of study treatment, or 30 days following cessation of study treatment, if the participant initiates new anticancer therapy, whichever is earlier.

### 9.3 Adverse Events, Serious Adverse Events and Other Reportable Safety Events

The definitions of an adverse event (AE) or serious adverse event (SAE), as well as the method of recording, evaluating, and assessing causality of AE and SAE and the procedures for completing and transmitting AE, SAE and other reportable safety event reports can be found in Appendix 4.

Progression of the cancer under study is not considered an adverse event as described in Section 9.3.5 – Disease-Related Events and/or Disease-Related Outcomes Not Qualifying as AEs or SAEs, and Appendix 4.

AE, SAEs, and other reportable safety events will be reported by the participant (or, when appropriate, by a caregiver, surrogate, or the participant's legally authorized representative).

The investigator, who is a qualified physician, and any designees are responsible for detecting, assessing, documenting, and reporting events that meet the definition of an AE or SAE as well as other reportable safety events. Investigators remain responsible for following up AE, SAEs and other reportable safety events for outcome according to Section 9.3.3.

#### 9.3.1 Time Period and Frequency for Collecting AE, SAE and Other Reportable Safety Event Information

All AEs, SAEs and other reportable safety events that occur after the consent form is signed but before treatment allocation/randomization must be reported by the investigator if the participant is receiving placebo run-in or other run-in treatment, if the event cause the participant to be excluded from the trial, or is the result of a protocol-specified intervention, including but not limited to washout or discontinuation of usual therapy, diet, or a procedure.

- All AEs from the time of treatment allocation/randomization through 30 days following cessation of study treatment must be reported by the investigator.
- All AEs meeting serious criteria, from the time of treatment allocation/randomization through 90 days following cessation of study treatment, or 30 days following cessation of study treatment if the participant initiates new anticancer therapy, whichever is earlier must be reported by the investigator.

The investigator must report all pregnancies and exposure during breastfeeding from the time of treatment allocation/randomization through

- 120 days following last dose of pembrolizumab and/or epacadostat OR
- 180 days after last dose of chemotherapeutic agents OR
- 30 days following cessation of study treatment if the participant initiates new anticancer therapy.

Additionally, any SAE brought to the attention of an investigator at any time outside of the time period specified above must be reported immediately to MSD if the event is considered to be drug-related.

Investigators are not obligated to actively seek AE or SAE or other reportable safety events in former study participants. However, if the investigator learns of any SAE, including a death, at any time after a participant has been discharged from the study, and he/she considers the event to be reasonably related to the study treatment or study participation, the investigator must promptly notify MSD.

All initial and follow-up AEs, SAEs and other reportable safety events will be recorded and reported to MSD or designee within the timeframes as indicated in [Table 15](#).

Table 15 Reporting Time Periods and Timeframes for Adverse Events and Other Reportable Safety Events

Type of Event	Reporting Time Period: Consent to Randomization/ Allocation	Reporting Time Period: Randomization/ Allocation through Protocol-Specified Follow-up Period	Reporting Time Period: After the Protocol Specified Follow-up Period	Timeframe to Report Event and Follow-up Information to MSD:
Non-Serious Adverse Event (NSAE)	Report if: - due to protocol-specified intervention - causes exclusion - participant is receiving placebo run-in or other run-in treatment	Report all	Not required	Per data entry guidelines
Serious Adverse Event (SAE) including Cancer and Overdose	Report if: - due to protocol-specified intervention - causes exclusion - participant is receiving placebo run-in or other run-in treatment	Report all	Report if: - drug/vaccine related. (Follow ongoing to outcome)	Within 24 hours of learning of event
Pregnancy/Lactation Exposure	Report if: - due to intervention - causes exclusion	Report all	Previously reported – Follow to completion/termination; report outcome	Within 24 hours of learning of event

Type of Event	Reporting Time Period: Consent to Randomization/ Allocation	Reporting Time Period: Randomization/ Allocation through Protocol-Specified Follow-up Period	Reporting Time Period: After the Protocol Specified Follow-up Period	Timeframe to Report Event and Follow-up Information to MSD:
Event of Clinical Interest (require regulatory reporting)	Report if: - due to intervention - causes exclusion	Report - Potential DILI - Require regulatory reporting	Not required	Within 24 hours of learning of event
Event of Clinical Interest (Do not require regulatory reporting)	Report if: - due to intervention - causes exclusion	Report - non-DILI ECIs and those not requiring regulatory reporting	Not required	Within 5 calendar days of learning of event

### 9.3.2 Method of Detecting AE, SAE and Other Reportable Safety Events

Care will be taken not to introduce bias when detecting AE and/or SAE and other reportable safety events. Open-ended and non-leading verbal questioning of the participant is the preferred method to inquire about AE occurrence.

### 9.3.3 Follow-up of AE, SAE and Other Reportable Safety Event Information

After the initial AE/SAE report, the investigator is required to proactively follow each participant at subsequent visits/contacts. All AE, SAE and other reportable safety events including pregnancy and exposure during breastfeeding, ECI, Cancer and Overdose will be followed until resolution, stabilization, until the event is otherwise explained, or the participant is lost to follow-up (as defined in Section 8.3). In addition, the investigator will make every attempt to follow all non-serious AEs that occur in randomized participants for outcome. Further information on follow-up procedures is given in Appendix 4.

### 9.3.4 Regulatory Reporting Requirements for SAE

- Prompt notification (within 24 hours) by the investigator to MSD of SAE is essential so that legal obligations and ethical responsibilities towards the safety of participants and the safety of a study treatment under clinical investigation are met.
- The Sponsor and MSD have a legal responsibility to notify both the local regulatory authority and other regulatory agencies about the safety of a study treatment under clinical investigation. All Adverse Events will be reported to regulatory authorities, IRB/IECs and investigators in accordance with all applicable global laws and regulations, ie, per ICH Topic E6 (R1) Guidelines for Good Clinical Practice.

- Investigator safety reports must be prepared for suspected unexpected serious adverse reactions (SUSAR) according to local regulatory requirements and MSD policy and forwarded to investigators as necessary.
- An investigator who receives an investigator safety report describing an SAE or other specific safety information (eg, summary or listing of SAE) from MSD will file it along with the Investigator's Brochure and will notify the IRB/IEC, if appropriate according to local requirements.

### **9.3.5 Disease-Related Events and/or Disease-Related Outcomes Not Qualifying as AEs or SAEs**

Efficacy endpoints as outlined in this section will not be reported to MSD, as described in Section 9.3.1. Specifically, the suspected/actual events covered in this exception include any event that is disease progression of the cancer under study.

MSD will monitor unblinded aggregated efficacy endpoint events and safety data to ensure the safety of the participants in the study. Any suspected endpoint which, upon review, is not progression of the cancer under study will be forwarded to MSD global safety as a SAE within 24 hours of determination that the event is not progression of the cancer under study.

### **9.3.6 Pregnancy and Exposure During Breastfeeding**

Although pregnancy and infant exposure during breastfeeding are not considered adverse events, any pregnancy or infant exposure during breastfeeding in a participant (spontaneously reported to the investigator or their designee) that occurs during the trial are reportable to MSD.

All reported pregnancies must be followed to the completion/termination of the pregnancy. Pregnancy outcomes of spontaneous abortion, missed abortion, benign hydatidiform mole, blighted ovum, fetal death, intrauterine death, miscarriage and stillbirth must be reported as serious events (Important Medical Events). If the pregnancy continues to term, the outcome (health of infant) must also be reported.

### **9.3.7 Events of Clinical Interest (ECI)**

Selected non-serious and serious adverse events are also known as Events of Clinical Interest (ECI) and must be reported to MSD.

Events of clinical interest for this trial include:

1. an overdose of study treatment, as defined in Section 9.4 – Treatment of Overdose, that is not associated with clinical symptoms or abnormal laboratory results.
2. an elevated AST or ALT lab value that is greater than or equal to 3X the upper limit of normal and an elevated total bilirubin lab value that is greater than or equal to 2X the upper limit of normal and, at the same time, an alkaline phosphatase lab value that is less than 2X the upper limit of normal, as determined by way of protocol-specified laboratory testing or unscheduled laboratory testing.\*

\*Note: These criteria are based upon available regulatory guidance documents. The purpose of the criteria is to specify a threshold of abnormal hepatic tests that may require an additional evaluation for an underlying etiology. The trial site guidance for assessment and follow up of these criteria can be found in the Investigator Trial File Binder (or equivalent).

It may also be appropriate to conduct additional evaluation for an underlying etiology in the setting of abnormalities of liver blood tests including AST, ALT, bilirubin, and alkaline phosphatase that do not meet the criteria noted above. In these cases, the decision to proceed with additional evaluation will be made through consultation between the study investigators and the MSD Clinical Director. However, abnormalities of liver blood tests that do not meet the criteria noted above are not ECIs for this study.

3. serotonin syndrome. The signs and symptoms of serotonin syndrome are described in Section 7.2.1.2.

## 9.4 Treatment of Overdose

### Pembrolizumab or Epacadostat Overdose

For this study, an overdose will be defined as  $\geq 1000$  mg ( $\geq 5$  times the dose) of pembrolizumab,  $\geq 1000$  mg of epacadostat daily, or as any dose  $\geq 20\%$  over the prescribed dose for the EXTREME regimen. No specific information is available on the treatment of an overdose of pembrolizumab or epacadostat. In the event of overdose, the participant should be observed closely for signs of toxicity. Appropriate supportive treatment should be provided if clinically indicated.

### Cetuximab Overdose

There is no available information for the treatment of a cetuximab overdose. In cases of greater than recommended doses, the AEs were similar to the known safety profile. Appropriate supportive treatment should be provided if clinically indicated.

Otherwise, overdose should be managed according to local label and practice.

### Carboplatin Overdose

There is no known antidote for carboplatin overdose. The anticipated complications of overdose may include myelosuppression and impairment of hepatic and renal function.

Otherwise, overdose should be managed according to local label and practice.

### Cisplatin Overdose

There is no specific antidote for cisplatin overdose. Overdose may result in the side effects associated with the drug occurring in an excessive manner.

Otherwise, overdose should be managed according to local label and practice.

### 5-fluorouracil Overdose

Signs and symptoms of 5-FU overdose are similar to the adverse reactions associated with the drug and should be managed according to local label and practice. Participants who have a 5-FU overdose should be closely monitored for 4 weeks.

Otherwise, overdose should be managed according to local label and practice.

If an AE(s) is associated with (“results from”) the overdose of study treatment, the AE(s) is reported as a SAE, even if no other seriousness criteria are met.

If a dose of study treatment meeting the protocol definition of overdose is taken without any associated clinical symptoms or abnormal laboratory results, the overdose is reported as a non-serious ECI, using the terminology “accidental or intentional overdose without adverse effect.”

All reports of overdose with and without an AE must be reported within 24 hours to MSD either by electronic media or paper. MSD Contact information can be found in the Investigator Trial File Binder (or equivalent).

## **9.5 Safety**

Planned time points for all safety assessments are provided in the SoA.

### **9.5.1 Physical Examinations**

#### **9.5.1.1 Full Physical Exam**

The investigator or qualified designee will perform a full physical exam as per institutional standard during the screening period. Clinically significant abnormal findings should be recorded as medical history. The time points for full physical exams are described in Section 2 - SoA. After the first dose of study treatment, new clinically significant abnormal findings should be recorded as AEs.

#### **9.5.1.2 Directed Physical Exam**

For cycles that do not require a full physical exam, as specified in Section 2 - SoA, the investigator or qualified designee will perform a directed physical exam as clinically indicated prior to the administration of the study treatment. New clinically significant abnormal findings should be recorded as AEs.

### **9.5.2 Vital Signs**

The investigator or qualified designee will take weight and vital signs at screening and as specified in Section 2 - SoA. Blood pressure and pulse measurements should be preceded by at least 5 minutes of rest for the participant in a quiet setting without distractions. Height will be measured at screening only.

### **9.5.3 Electrocardiograms**

Baseline ECGs will be obtained at screening with additional ECGs obtained at EOT, and as clinically indicated for all participants. At select centers only, additional ECGs will also be obtained from Group 1 participants at Cycle 1 Day 1 predose and 2 hours ( $\pm$  15 minutes) after the first dose of epacadostat and Cycle 2 Day 1 predose and 2 hours ( $\pm$  15 minutes) after administration of epacadostat. The ECG measurement should always be performed prior to the PK sample blood draw if both are scheduled at the same nominal planned timepoint. Clinically significant abnormal findings prior to signing consent should be recorded as

medical history. Clinically significant abnormal findings after signing consent should be recorded as an AE.

The ECGs will be interpreted by the investigator at the site and will be used for immediate participant management. The decision to include or withdraw a participant from the study based on an ECG flagged as "Abnormal, Clinically Significant" is the responsibility of the investigator, in consultation with the MSD Clinical Director, as appropriate. The Fridericia (preferred) or Bazett correction method for calculating QTc will be used and recorded in the eCRF.

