Pembrolizumab Administration at Site		X	X	X	X	X			Cycle 1 treatment should be given within 5 days of randomization.
Dispense Epacadostat (Group 1 only)		X	X	X	X	X			
Epacadostat Administration at Site (Group 1 only)		X	X						Only morning dose will be administered at site.
Collect and Count Remaining Epacadostat (Group 1 only)			X	X	X	X	X		
Efficacy Procedures/Assessments									
Tumor Imaging and RECIST Assessments	X				X		Per Standard of Care		Imaging should be performed at Week 9 (+7 days) after randomization. Thereafter imaging is to be performed as per SoC for the disease and local guidelines; only the date of scans performed as per SoC needs to be documented in the eCRF. Schedule should be followed regardless of treatment delays.

Study Period	Screen	Treatment (3-week cycles)					EOT	Post-treatment	Notes
Treatment Cycle/Title	Screen (V 1)	1	2	3	4	Cycle 5 to Cycle 35	Discon	Safety FU	
Scheduled Window (Days):	-28 to -1	+5	±3	±3	±3	±3	At treatment discon	30 days after last dose (+7 days)	Assessments/procedures are to be performed on Day 1 and prior to the first dose of treatment for each cycle unless otherwise specified. Participants who discontinue study treatment for whatever reason will proceed directly to EOT and Safety Follow-up.
Safety Procedures/Assessments									
Full Physical Examination	X						X		
Directed Physical Examination		X	X	X	X	X		X	
Height	X								
Vital Signs and Weight	X	X	X	X	X	X	X	X	Vital signs to include temperature, pulse, respiratory rate and blood pressure.
ECOG PS	X	X	X	X	X	X	X	X	ECOG PS is to be performed within 7 days of randomization and must be 0 or 1 on the first day of dosing.
12-lead ECG (Local)	X						X		ECGs at screening and EOT are required for all participants. ECGs should also be done when clinically indicated.
12-lead ECG (Local; Group 1 at select sites only)		X	X						Predose and 2 hours (±15 minutes) after the morning dose of epacadostat.
Pregnancy Test Serum or Urine (WOCBP only)	X								WOCBP require negative test within 72 hours prior to Cycle 1 Day 1. Monthly (ie, before each cycle) pregnancy testing should be conducted as per local regulations where applicable.
Coagulation	X								Any participant receiving anticoagulant therapy should have coagulation factors monitored closely throughout the study.

Study Period	Screen	Treatment (3-week cycles)					EOT	Post-treatment	Notes
Treatment Cycle/Title	Screen (V 1)	1	2	3	4	Cycle 5 to Cycle 35	Discon	Safety FU	

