### 10.6.2 Statistical Methods for Safety Analyses

Safety and tolerability will be assessed by clinical review of all relevant parameters including AEs, laboratory tests, vital signs, and ECG measurements.

Individual events and the broad AE categories consisting of the proportion of participants with any AE, a drug related AE, a serious AE, an AE which is both drug-related and serious, a Grade 3-5 AE, a drug related Grade 3-5 AE, a fatal AE, dose interruption due to an AE and discontinuation due to an AE, will be summarized by counts and percentages by treatment group (Table 18).

Table 18 Analysis Strategy for Safety Endpoints

Safety Endpoint	Descriptive Statistics
Any AE	X
Any Serious AE	X
Any Grade 3-5 AE	X
Any Drug-Related AE	X
Any Serious and Drug-Related AE	X
Any Grade 3-5 and Drug-Related AE	X
Dose Interruption due to AE	X
Discontinuation due to AE	X
Death	X
Specific AEs, SOCs	X
Change from Baseline Results (lab toxicity grade)	X

Abbreviations: AE = adverse event;

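### Four scheduled ECGs at select sites in Group 1 have no scheduled Group 2 counterpart, so ECG and cardiac AE percentages are not like for like between these arms

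*Combined protocol and SAP*

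**What the plan says.** Groups 1 and 2 share one Schedule of Activities (Section 2.1.1). Its general ECG note reads: "ECGs at screening and EOT are required for all participants. ECGs should also be done when clinically indicated". A separate row, headed "12-lead ECG (Local; Group 1 at select sites only", is marked in Cycles 1 and 2 only. Section 9.5.3 agrees with it: "At select centers only, additional ECGs will also be obtained from Group 1 participants at Cycle 1 Day 1 predose and 2 hours" after the first epacadostat dose, then "Cycle 2 Day 1 predose and 2 hours" after dosing.

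Section 9.5.3 also sets the recording rule, "Clinically significant abnormal findings after signing consent should be recorded as an AE", and says who reads the tracing: "The ECGs will be interpreted by the investigator at the site and will be used for immediate participant management". The study is open-label (Section 7.4). Under Section 9.3.1, AE reporting runs from randomization.

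On analysis, Section 10.6.2 says: "Safety and tolerability will be assessed by clinical review of all relevant parameters including AEs, laboratory tests, vital signs, and ECG measurements". Table 18 then lists the AE categories to be tabulated descriptively for each arm. It has no row for ECG measurements; its only change-from-baseline row concerns laboratory toxicity grade. Nothing in Section 10 treats AEs found on the select-site ECGs differently from other AEs.

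**The concern.** An ECG abnormality without symptoms is found only when an ECG is done. If one arm is examined more often by schedule, its AE percentage for such findings can be higher with no difference in true risk.

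Group 1 against Group 2 is where this matters. Sections 5.1 and 5.4 say that the monotherapy arm is there to show what epacadostat adds, and since Amendment 04 safety is the only secondary objective. A reader who compares the cardiac rows of these two arms will be inclined to attribute a difference to epacadostat. Because Table 18 has no ECG row, within that table ECG findings can appear only as AEs, which is the route affected by the unequal schedule.

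One of the four extra ECGs precedes any epacadostat. A new finding there cannot be an effect of that drug, yet it is reportable and Section 10 has no rule that keeps it apart.

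**Working it through.** **Plan figures.** Section 10.9 plans about 90 participants at 2:1:2. 90 × 2/5 = 36, 90 × 1/5 = 18 and 90 × 2/5 = 36, as stated. The 89 randomized give 35.6, 17.8 and 35.6 on the same ratio. The documents state no figure for ECG-detected AEs.

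**Schedule count** (Sections 2.1.1 and 9.5.3), scheduled ECGs per participant:

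| | Screening | Cycle 1 Day 1 | Cycle 2 Day 1 | EOT | After randomization |
|---|---|---|---|---|---|
| Group 1, select sites | 1 | 2 | 2 | 1 | 5 |
| Group 1, other sites | 1 | 0 | 0 | 1 | 1 |
| Group 2 | 1 | 0 | 0 | 1 | 1 |

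**Assumptions.** Let f be the share of Group 1 at select sites and q the chance per ECG of a finding called clinically significant. The documents give neither. I take f = 25%, 50% and 100%, q = 0.5% to 5%, equal true risk in both arms, and independent ECGs within a participant.

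**Per participant.** The chance of at least one flagged scheduled ECG after randomization is 1 − (1 − q)^5 at select sites and q in Group 2. At q = 0.5% this is 2.5% against 0.5% (ratio 4.95). At q = 5% it is 22.6% against 5% (ratio 4.52).

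**Per arm.** Expected Group 1 participants with a flagged finding on the four extra ECGs = 36 × f × (1 − (1 − q)^4). The last factor is 0.0199 at q = 0.5% and 0.1855 at q = 5%.

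| f | q = 0.5% | q = 5% |
|---|---|---|
| 25% | 0.2 (0.5 points) | 1.7 (4.6 points) |
| 50% | 0.4 (1.0 points) | 3.3 (9.3 points) |
| 100% | 0.7 (2.0 points) | 6.7 (18.5 points) |

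Some of these would also be flagged at EOT, which Group 2 has too. Removing them multiplies each entry by (1 − q), so the largest becomes 6.68 × 0.95 = 6.3. Counting only the three ECGs after first exposure to epacadostat (exponent 3), the range before that adjustment is 0.1 to 5.1 participants.

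**The Any AE row.** A participant who already has another AE is not counted twice, so the shift is f × (1 − (1 − q)^4) × (1 − b), where b is the proportion with another AE. At f = 100% and q = 5%, treating the two as independent:
- b = 95%: 18.5 × 0.05 = 0.9 points.
- b = 90%: 18.5 × 0.10 = 1.9 points.
- b = 64%: 18.5 × 0.36 = 6.7 points.

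The 64% is the treatment-related AE rate in an earlier pembrolizumab monotherapy study (Section 3.2.3). It is a low anchor, because it leaves out unrelated AEs.

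**Scale.** Exact 95% intervals are 0.1% to 14.5% for 1 of 36 and 0% to 18.5% for 0 of 18. One or two cases produced by the schedule could make a sparse cardiac row look different between the arms.

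**The case against.** The strongest reply is that nothing here is shown to be inflated. Group 2 can have ECGs when clinically indicated. Only findings that the investigator calls clinically significant are recorded. The number of select-site participants is unknown and may be small. All of this stands, and it rules out the stronger statement that a reader might infer, namely that Group 1's AE rows are inflated. The documents support only that certain rows can be.

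The 22.6% is also easy to misread as an estimate. It applies to one select-site participant, rests on a 5% rate that no document anchors, and treats the ECGs as independent although they include two same-day pairs. With findings that persist from one ECG to the next, the excess would be smaller, since some would also be seen at EOT. Eligibility ECGs are done within 10 days before first dose and a QTc limit applies (exclusion criterion 31), so the same q on the Cycle 1 predose ECG is doubtful. The high end is an extreme.

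Safety reporting is descriptive, with no test and no planned difference between arms. That limits the consequence, but readers will still compare the columns.

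Redacted sections may explain these ECGs: Section 9.5.3 mentions PK draws at the same nominal times, and contents entries before Section 9.9 are blacked out. However, Section 10.1 places the comprehensive analysis plan in Sections 10.2 to 10.12, and that text appears complete.

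Finally, onset time and attribution are already recorded for AEs (Section 5.4.1.2). This makes the remedy cheap; it does not make it part of the plan.

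**Conclusion.** The point holds as a minor one. By schedule, select-site Group 1 participants have four more ECGs than Group 2 participants, and clinically significant findings enter the by-arm AE counts unseparated. ECG and cardiac-specific percentages are therefore not like for like between Groups 1 and 2, and any bias from the extra looks runs towards Group 1.

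The size cannot be derived from the documents. Under the assumptions above it runs from well under one to about seven of 36 participants, and it shrinks with a smaller select-site share or correlated findings. The Any AE row should move little when most participants have another AE, and routine ECGs are unlikely to drive the SAE or death rows.

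Two wider readings are not supported. The documents do not show that a cardiac excess in Group 1 would be only an artefact; they show only that the planned tables could not tell. Nor does the point extend to Group 3, where unequal looking does not run one way: that arm has weekly visits in Cycles 1 to 4, with vital signs and, from Day 8, laboratory tests. The ORR analysis and its precision are unaffected.

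**What to change.** In Section 10.6.2 and Table 18:

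1. Report how many Group 1 participants had the select-site ECGs.
2. Flag AEs first detected only on those ECGs, and mark separately any found on the Cycle 1 predose ECG, before any epacadostat.
3. Show the ECG and cardiac AE rows with and without the flagged events. No AE is dropped from the main table.
4. If a by-arm summary of ECG measurements is produced (Table 18 does not plan one), restrict the Group 1 against Group 2 comparison to the timepoints both arms share. List the select-site results for Group 1 alone.

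The cost is one flag linking an AE to the ECG on which it was first seen, which may need a short review of AEs with onset on those days, and one extra table. No procedure, visit or clinical rule changes.
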